## Study Procedures

After informed consent is obtained, participants will undergo standard clinical examination and thorough medical history. This evaluation will be used to assure clinical stability and that the

subject meets all inclusion criteria. Along with the baseline exercise test, questionnaires will be administered regarding current and past physical activity patterns, quality of life, and symptoms. Fasting blood labs will be obtained on a different day than the exercise test.

**Cardiopulmonary Exercise Testing.** Peak  $VO_2$  will be determined at baseline and after 6 months and 1 year on a treadmill using an individualized ramp protocol with collection of continuous ventilatory gas exchange responses. A thorough clinical history, medications and risk factors will be recorded prospectively at the time of baseline exercise testing using computerized forms that include standard definitions of clinical conditions and exercise responses. In accordance with standard practice at the Palo Alto VAHCS, prior to exercise testing, patients complete a questionnaire to estimate exercise capacity; the questionnaire is used to individualize the exercise protocol which allows most patients to reach maximal effort within the recommended range of 8 to 12 minutes (58). We previously observed that this protocol provides the closest relation between measured and estimated metabolic equivalents (METs) (59). Patients will be discouraged from using the handrails for support. Medications will not be changed or stopped prior to testing. A 12-lead electrocardiogram, heart rate, and blood pressure responses will be monitored throughout the exercise test and recovery period. Ventilatory gas exchange measurements will be obtained continuously at rest, throughout exercise, and during 5 minutes of recovery. All subjects will be encouraged to give a maximal effort, and the Borg 6-20 scale will be used to quantify subjective effort (60). Standardized clinical indications for stopping will be used. ST-segment depression will be measured visually at the J junction, and slope will be determined over the following 60 ms and classified as upsloping, horizontal, or downsloping. Ventricular tachycardia will be defined as three or more consecutive premature ventricular contractions, and *frequent* premature ventricular contractions will be defined as 10% or more of the total ventricular contractions. Blood pressure will be measured manually, and exercise capacity will be measured directly using ventilatory gas exchange techniques. The exercise tests will be performed, analyzed, and reported according to a standardized protocol and utilizing a computerized database (61).

The Duke Treadmill Score (62) and the VA Prognostic Score (63) will be used to help estimate risk and assess suitability for exercise training. The American Heart Association Guidelines on Exercise Testing (64) recommend that the Duke Score, which incorporates ischemic responses, symptoms, and exercise capacity, be used for all clinical exercise testing to stratify risk. The VA Prognostic Score was developed at the VA Palo Alto HCS and incorporates pre-and post-test responses that have been shown to powerfully estimate risk in Veterans referred for exercise testing (63). Patients with evidence of significant coronary artery disease as determined by profound ischemic markers, ominous arrhythmias, resting ECGs that confound the recognition of ischemia (bundle branch block, more than 1 mm ST depression, paced rhythm) will be excluded. Patients with hemodynamic instability or inability to exercise, those with complicating illnesses or questionable motivation to sustain prolonged training will also be excluded.

**Exercise Training.** Initially, all subjects will undergo supervised exercise sessions 3 times weekly over a 2 month period. The purpose of these sessions will be to familiarize the patients to their individualized training program, assess stability during exercise, ascertain that they understand their exercise prescription and how to use activity and heart rate logs, and provide guidelines and education in terms of what is expected of them during the study. Subjects will then exercise at home, with an in-house exercise session repeated every 2 weeks for the duration of the study. The biweekly exercise sessions will be used to ensure stability and compliance, to review activity logs, and to modify the exercise prescription as appropriate. Guidelines for patient monitoring, safety, and prescription outlined by the American Heart Association, American College of Sports Medicine, and American Association of Cardiovascular and Pulmonary Rehabilitation will be followed (64,65,66). The exercise sessions will include 5 minute warm-up and cool-down sessions prior to and following a combination of continuous aerobic (treadmill walking, cycle ergometry, arm ergometry, rowing, stair climbing) and resistance exercise. Exercise intensities will initially be targeted to achieve 60% of heart rate reserve for duration of 30 minutes; exercise intensity will be documented for each patient by frequent (5 minute) recordings of heart rate and

issued as needed. A parallel goal will be to achieve 2,000 kcals/week of energy expenditure based on the VETS 7-Day Recall Questionnaire; this amount is the equivalent of approximately 1 hour of moderate activity most days of the week. This amount has been a benchmark in epidemiologic studies both in the VA and other populations, and has been shown to have a strong inverse relation with mortality and cardiac events (24,31,68).

### **Blood Panels**

Standard blood labs and lipid panels including total cholesterol, LDL, HDL, ApoB, lipoprotein(a), C-reactive protein, fasting glucose, and triglycerides will be determined at *baseline, every 4 months, and at 1 year for both groups*. All analyses will be performed by the VA Clinical Laboratory.

### **Questionnaires**

A synopsis of the questionnaires instruments to be used in the study is presented in Appendix II.

**Physical Activity Questionnaires.** During screening, physical activity patterns will be quantified in all subjects. Quantification of activity will be performed using the VA Physical Activity Questionnaire (VAPAQ), an instrument that has been used extensively by Drs. [name] and [name] over the last 20 years (31). The questionnaire is conducted by an experienced staff member through a detailed interview and takes about 15 minutes. Metabolic costs of occupational and recreational activities will be computed, and energy expenditure will be expressed in kilocalories per week. Energy expenditure will be expressed in terms of lifetime adulthood recreational and occupational activity. Recreational activity will also be expressed separately as energy expended during the year before baseline testing (recent activity).

In addition to the initial VA activity questionnaire, all subjects will record daily activities throughout the study using a daily exercise log (recorded by each subject, Appendix III), and the Veterans Exercise Testing Study 7 Day Activity Recall (recorded weekly by interview with staff member, Appendix IV). The daily logs will record compliance to the exercise regimen and quantify any changes in physical activity that take place during the study.

[figure not shown]
**Symptom Questionnaire.** Symptom relief is an important outcome associated with both PCI and exercise intervention, and angina symptoms will be monitored closely throughout the study. The Seattle Angina Questionnaire (69) will be used to quantify angina symptoms, and any changes in symptoms, at 3 month intervals. The Seattle Angina Questionnaire was developed and originally validated among veterans. It is a widely validated instrument that measures five clinically important dimensions of health in patients with CAD. It has been shown to be sensitive to clinical change and is considered a reliable instrument for measuring clinical outcomes in patients with CAD.

**Quality of Life.** Quality of life will be assessed at baseline, 6-months and 1 year using the standard SF-36 questionnaire (70). The SF-36 provides an 8-scale profile of functional health and well-being scores as well as psychometrically-based physical and mental health summary measures and a preference-based health utility index. This tool has been used in several thousand clinical studies and has proven useful in surveys of general and specific populations, comparing the relative burden of diseases, and in differentiating the health benefits produced by a wide range of different treatments.

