PCI is often the preferred choice for patients and providers for immediate symptomatic relief despite lack of evidence supporting a mortality benefit with PCI. The potential value of rehabilitation is underscored by the observation that outcomes are improved among patients who participate in such programs (18,19,24,35-37). A recent Cochrane meta-analysis demonstrated a 27% reduction in total mortality and a 31% reduction in cardiac mortality among patients randomized to exercise training compared to usual care (35). This is in agreement with earlier meta-analyses of randomized trials performed in the 1970s and 1980s, demonstrating reductions in cardiovascular morbidity and mortality from 20 to 30% among subjects randomized to rehabilitation (36,37). The benefits of exercise and lifestyle changes have also been documented by direct comparison to an interventional strategy; in the widely-cited Leipzig study, 12 months of exercise training in stable CAD patients was associated with better event-free survival, better coronary anatomy, and lower costs as compared to PCI (12). Although PCI has well-documented benefits for symptom relief, mortality benefits with PCI have not been demonstrated. A recent meta-analysis of 61 controlled trials reported that PCI had no benefit on mortality or myocardial infarction compared to medical therapy in non-acute coronary artery disease (38). Although exercise and lifestyle intervention have well-documented benefits on cardiovascular morbidity and mortality (4,12,18,24,26,35), this approach is rarely applied in candidates for PCI. The current proposal could provide an impetus to refer patients to rehabilitation programs as a complement to PCI (39), or as an alternative to PCI in selected patients (12). Our hypothesis is that a program of exercise-based rehabilitation will have greater improvement in overall coronary anatomy and myocardial perfusion and result in better outcomes, improved quality of life and will be more cost effective than PCI alone.

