### ***Statistical Analysis Plan***

***Key Question #1:*** Does exercise training favorably alter coronary anatomy and function as determined by non-invasive imaging techniques?

***Statistical Analysis, Key Question #1.*** Myocardial blood flow using PET at rest and following dipyridamole infusion will be expressed as ml flow/100 g/min. The primary outcome, myocardial perfusion reserve, will be calculated as the ratio of the myocardial blood flow during stress (e.g. after dipyridamole) and the myocardial blood flow at rest. Differences within and between groups will be assessed using repeated measures ANOVA, with group (exercise vs. PCI) and test (baseline vs. 1-year) as factors. Post-hoc procedures will be performed using the Bonferonni method.

***Key Question #2:*** Can a program of exercise therapy improve outcomes (exercise capacity, symptoms, repeat hospitalizations, and quality of life) in patients with CAD that are equivalent or superior to PCI?

Statistical Analysis, Key Question #2. These secondary outcomes will include changes in peak  $VO_2$  and other cardiopulmonary exercise test responses (including  $VO_2$  at the ventilatory threshold, exercise time, and heart rate recovery), quality of life measures, and lipid panels. Paired tests will be used (paired t-test or Wilcoxon signed rank test) to compare continuous variables between groups at baseline. Differences between groups after the 1-year study period will be assessed by repeated measures ANOVA, with group (exercise vs. PCI) and test (baseline vs. 1-year) as factors. Post-hoc procedures will be performed using the Bonferroni method.

**Key Question #3:** Will exercise training reduce costs as compared to standard PCI after 1-year?

Statistical Analysis, Key Question #3. Comparison of costs will be made for the individual level change scores using the intervention net-costs (intervention delivery minus healthcare expense cost-savings). Cost effectiveness of the intervention will be defined by the primary outcome at the patient level. That is, changes from baseline in individual global myocardial perfusion reserve using PET at 1-year will be used to calculate the effect. Differences in costs between groups will be assessed using ANOVA.

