**Table 1: Schedule of measurements.**

Measurement	Baseline	4 Months	6 Months	8 Months	1-Year
- Vitals, weight & physical exam	√	√	√	√	√
Fasting Bloods					
- Lipid Panel, standard Chem 20	√	√		√	√
- Hemoglobin A1c, CRP	√	√		√	√
Fitness and Functional Capacity					
- Cardiopulmonary Exercise Test	√		√		√
- Strength, Waist/Hip ratio	√		√		√
Myocardial Perfusion					
- PET/CTA	√				√
Questionnaires					
- VA Physical Activity Ques.	√		√		√
- VETS 7-Day Activity Recall*	√	weekly	weekly	weekly	weekly
- Seattle Angina Questionnaire	√		√		√
- SF-36 Quality of Life	√		√		√

\* Activity logs will be kept daily throughout the study, with the questionnaire performed weekly

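### Angina symptoms and repeat hospitalisation in Key Question #2: two conflicting questionnaire schedules, and no analysis named for either outcome

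*Combined protocol and SAP*

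**What the plan says.** **Schedule.** The Symptom Questionnaire paragraph under Questionnaires says that the Seattle Angina Questionnaire "will be used to quantify angina symptoms, and any changes in symptoms, at 3 month intervals". In Table 1, the row "Seattle Angina Questionnaire" has three ticks, in the same pattern as the SF-36 row: baseline, 6 months and 1 year. The table's columns are baseline, 4, 6 and 8 months, and 1 year, so it has no place for a 3- or 9-month assessment.

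**Outcomes.** Key Question #2 in the Statistical Analysis Plan asks: "Can a program of exercise therapy improve outcomes (exercise capacity, symptoms, repeat hospitalizations, and quality of life) in patients with CAD". The analysis paragraph beneath it lists peak VO2 and other exercise-test responses, then "quality of life measures, and lipid panels". Symptoms and hospitalisations do not appear.

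**Method.** The only between-group method given for this question at follow-up is: "Differences between groups after the 1-year study period will be assessed by repeated measures ANOVA, with group (exercise vs. PCI) and test (baseline vs. 1-year").

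**Analysis set and data source.** Sample Size Estimates expects 20% dropout and removes dropouts from the analyses. The cost section (VA Utilization Extractions and Cost-Savings Estimates) follows hospitalisations and other use of care in VA records for each patient in the trial. It arranges these into one-year periods before and after the intervention.

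**Context.** Significance of the Current Proposal says that "PCI is often the preferred choice for patients and providers for immediate symptomatic relief".

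**The concern.** Staff who work from Table 1 will not collect the 3- and 9-month angina scores that the text promises, and those scores cannot be recovered later. Two of the four outcomes in Key Question #2 have no named analysis, so the method could be chosen after the data are seen.

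If the stated ANOVA is applied by default, the symptom comparison rests on 1 year alone. Any early difference is left out, although the protocol itself gives rapid relief as a reason for choosing PCI. For hospitalisation, a baseline-visit versus 1-year-visit factor does not match the nature of the outcome. Admissions among subjects who leave the study would also be lost, and an admission may itself be a reason for leaving.

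**Working it through.** **1. The plan's own figure.** The only sample size stated is for the primary endpoint.
- SD of change = √(2 × 0.20² × (1 − 0.65)) = 0.167.
- Standardised effect = 0.135 / 0.167 = 0.81. At two-sided 0.05 and 80% power this gives 25 per group.
- 25 / 0.80 = 31.25, rounded up to 32 per group, 64 in all.

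The figure reproduces and this point does not affect it. With 25 per group, any continuous score, including an angina score, has 80% power only for a standardised difference of about 0.81.

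**2. Angina assessments.**

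| Source | Post-baseline times | Number | Used by a baseline vs 1-year ANOVA | Unused |
|---|---|---|---|---|
| Questionnaires text | 3, 6, 9, 12 months | 4 | 1 | 3 |
| Table 1 | 6, 12 months | 2 | 1 | 1 |

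A PDF reading fault does not explain the Table 1 row. It matches the SF-36 row, and the Quality of Life paragraph confirms the SF-36 times in words.

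**3. Outcomes asked about against outcomes listed for analysis.**

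| Named in Key Question #2 | Named in its analysis paragraph |
|---|---|
| Exercise capacity | Yes |
| Symptoms | No |
| Repeat hospitalisations | No |
| Quality of life | Yes |

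Lipids are listed for analysis although the question does not name them.

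**4. How hospitalisation data would look.** The documents give no rate. Assume Poisson rates of 0.1 to 0.4 per subject per year. The share with no admission in a year is then e^(−0.1) = 90% down to e^(−0.4) = 67%, so most values are zero. In a simulation with 25 per arm and no true difference, a comparison of change in yearly counts rejected in 4.6% to 5.1% of runs at a nominal 5%. A comparison of post-year counts with extra between-subject variation rejected in 3.3% to 4.3%. False positives are therefore not the difficulty. The method uses neither the timing of events nor the length of follow-up.

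**5. Exclusion of dropouts.** 20% × 64 = 12.8, about 13 randomised subjects. This counts subjects left out, not admissions lost, because no admission rate is given.

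**6. Index admission.** No definition of a repeat hospitalisation is given. At the assumed rates, 32 subjects would have 32 × 0.1 = 3.2 to 32 × 0.4 = 12.8 admissions in a year. If each PCI subject's index procedure counted as one admission, up to 32 would be added to that arm alone.

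**7. Power for hospitalisation.** The proportions admitted are assumed. With p̄ the mean of the two proportions, n per arm = [1.96√(2p̄(1−p̄)) + 0.8416√(p₁(1−p₁) + p₂(1−p₂))]² / (p₁−p₂)². For 30% vs 15%: (1.157 + 0.489)² / 0.0225 = 120.5, so 121.

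| Assumed proportions | n per arm for 80% | Power, 25 per arm | Power, 32 per arm |
|---|---|---|---|
| 40% vs 20% | 82 | 34% | 41% |
| 30% vs 15% | 121 | 24% | 30% |
| 20% vs 10% | 199 | 16% | 20% |

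**The case against.** The strongest reply is that little is truly missing. The analysis list is worded as inclusive, so it need not be complete, and the question just above it names symptoms. Both schedules give an angina score at baseline and at 1 year, so the stated ANOVA can be run on it. The cost section builds a year before and a year after for each patient, so even hospitalisations have a form of pre/post pair. A 1-year comparison is also a legitimate question to ask, and all of this concerns secondary outcomes.

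Much of that stands, and it rules out several stronger readings that a reader might infer:

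- **That the ANOVA cannot handle hospitalisations.** It could be computed on the yearly counts and would roughly keep its error rate (step 4). It is unsuited and unspecified, not impossible.
- **That symptoms cannot be analysed as planned.** They can, at 1 year. The loss is the interim scores and a named analysis.
- **That the protocol calls symptom relief the main benefit of PCI.** It gives quick relief as a reason PCI is preferred and does not rank it. It also credits PCI with reducing ischaemia, and it calls symptom relief important for both treatments.
- **That a 1-year comparison is biased towards exercise by a known amount.** The documents give no time course for angina scores, so no bias can be sized.

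The reply does not remove the schedule conflict. Nor does it help to read the angina questionnaire as a quality-of-life measure, because the protocol assigns quality of life to the SF-36 and places symptoms under a separate heading. The pre/post counts were set up for costing, and nothing carries them into Key Question #2. The exclusion of dropouts is a general rule, but it is least defensible for an outcome that can be followed in records after a subject leaves the study.

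**Conclusion.** The point holds as a secondary-outcome defect that should be corrected. The two angina schedules conflict, four post-baseline assessments against two, and the documents do not show which is intended. Two of the four outcomes in Key Question #2 are absent from its analysis text. Its one method leaves one or three of the post-baseline angina scores unused, depending on the schedule. For hospitalisation that method fits poorly, and the completer rule would remove about 13 of 64 subjects whose records are tracked anyway.

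The counts in steps 2 and 3 come straight from the documents, and the 13 rests on the planned 20% dropout. The share of zeros, the error rates and the power figures rest on assumed hospitalisation rates and are illustrations only. The primary endpoint and its sample size are untouched.

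**What to change.** 1. Reconcile the Symptom Questionnaire paragraph and Table 1 to one angina schedule. If the 3-month schedule is kept, the weekly calls already planned for all subjects (Monitoring Phone Calls) could carry the extra assessments.
2. Name symptoms and repeat hospitalisation in the Key Question #2 analysis.
3. Analyse all angina scores in a mixed model with a group-by-visit term. Report the contrast at the first post-baseline visit as well as at 1 year.
4. Define repeat hospitalisation and count it from randomisation in all randomised subjects, using the VA records. Analyse it as time to first event or as a rate per person-year. State whether the index PCI admission counts, since counting it adds events to the PCI arm only; the sponsor must decide this before data are seen.
5. Present the hospitalisation result as an estimate with a confidence interval.

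The cost is a revised table, some SAP wording, a little more analysis and possibly a short questionnaire at two more time points. The change does not make the hospitalisation question well powered. With all 32 per arm, power is about 20% to 41% under the assumed proportions above.

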### **PET/CTA Study Protocol**

**Rationale and Accuracy of PET/CTA in the Proposed Study.** *Our objective is to demonstrate that exercise training, an intervention that improves coronary artery endothelial function, can improve myocardial perfusion to a degree that is similar to PCI, an intervention that decreases*

localized vessel obstruction. Both interventions improve myocardial perfusion (see figure), but they have not been previously compared, particularly in a randomized fashion. Myocardial perfusion reserve determined by PET will be the primary outcome measure. It is defined as the ratio of myocardial perfusion during stress to myocardial perfusion at rest. Myocardial perfusion reserve provides information on the functional significance of anatomic stenosis and assesses the ability of the coronary arteries to dilate. It is a well-validated measure of changes in myocardial blood flow both during rest and stress conditions. It has been shown to be a precise correlate of the degree of coronary artery disease, with a predictive accuracy that is superior to other non-invasive techniques (64,71,72). Quantification of myocardial perfusion can be performed with chemical (72-76), exercise (77), or psychological (55) stress, and these methods have been employed to study myocardial blood flow by the investigators of the current proposal. While only a year of training is unlikely to demonstrate changes in coronary atheroma obstruction similar to PCI, it has been shown to improve the ability of arteries to dilate very quickly (ie, within weeks).

A global rather than a regional measure is preferred because a regional method could miss the global improvement in myocardial perfusion associated with exercise training. PCI treats the target lesion; specifically, it lessens the obstruction of the stenotic epicardial artery, resulting in regional flow improvement reflected in global changes. Thus, the most equitable comparison is a measure of overall myocardial perfusion and not just the perfusion of the territory supplied by the stenotic artery.

In addition, we have chosen myocardial perfusion reserve measured during hyperemia because previous studies have shown improvements in myocardial perfusion reserve following either exercise training (78) or PCI (79), and this type of stress is more convenient and reliable than other stresses. Exercise training, with durations ranging from 4 weeks to 1 year, has been shown to improve coronary endothelial function measured by invasive angiography (19) and myocardial perfusion measured by PET (78). The latter study was a small evaluation of 7 patients using PET perfusion; the investigators reported a 20% improvement in myocardial perfusion reserve after 14 weeks of exercise training. In one study among patients evaluated before and after receiving PCI, a 20% improvement in myocardial perfusion measured by PET was observed (79). However, a randomized controlled trial to determine whether exercise or PCI provides greater improvement in myocardial perfusion has not been performed.

PET perfusion imaging has also been shown to be highly reproducible. In repeat studies of coronary blood flow and coronary flow reserve, the slope of the correlation lines have been shown to be 0.98 and 0.96, respectively, with inter- and intra-observer reliabilities of 0.97 (80). The diagnostic accuracy of PET has been reported in many studies; the table below summarizes the accuracy of PET compared with invasive coronary angiography. Note that the weighted summary shows an overall predictive accuracy of 0.90, higher than other non-invasive methods for detecting coronary artery disease.

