## **Key Questions and Hypotheses**

### **Key Questions**

- 1) Does exercise training favorably alter coronary anatomy and function as determined by non-invasive imaging techniques?
- 2) Can a program of exercise therapy improve outcomes (exercise capacity, symptoms, repeat hospitalizations, and quality of life) in patients with CAD that are equivalent or superior to PCI?
- 3) Will exercise training and intensive risk reduction reduce costs as compared to standard PCI after 1-year?

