### **Sample Size Estimates**

*Sample size estimates are based on our primary endpoint, change in global myocardial blood flow reserve from baseline using pharmacologic stress with dipyridamole, and applying variance in myocardial blood flow reserve measured by PET published previously in subjects with coronary artery disease (71,77,78). We anticipate that the overall change in the primary endpoint will be approximately 15%; this is based on previous measurements of coronary blood flow reserve using PET comparing sedentary and fit subjects cross-sectionally (77), after exercise training (78), and risk reduction interventions such as smoking cessation (96). We also anticipate that these changes will parallel the well-documented changes in exercise capacity with training in subjects with CAD (i.e. mean change in peak  $VO_2 \approx 15\%$ ) (18,19,24). Given a standard deviation of myocardial flow reserve in similar populations of 0.20 ml/g/min both at baseline and after treatment with a pre-post correlation of 0.65 (calculated from the data in reference 96), the standard deviation of the change in myocardial blood flow is 0.167. We want to detect a 15% change (absolute change of  $0.15 \times 0.9$  or 0.135) so the standardized effect size (absolute value of difference in group values for mean change divided by the standard deviation) is about 0.81. Using a 2-sided significance level of 0.05 and 80% power, 25 subjects in each group will be needed to complete the protocol.*

We anticipate that there will be a 20% dropout rate, which is typical of that in the cardiac rehabilitation literature and in accordance with our previous experience. Thus, our target enrollment will be 32 subjects in each group. The dropout rate may be lower given that compliance tends to be better in research studies compared to clinical practice, and that the subjects will receive continuous monitoring, follow-up, and encouragement to remain physically active. *Dropouts will not be included in the statistical analyses (97).*

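### The plan speaks of perfusion gains similar to PCI and outcomes equivalent to PCI, but sets no margin and plans only difference tests, which cannot support either claim

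*Combined protocol and SAP*

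**What the plan says.** Most of the document asks whether exercise does better than PCI. The primary aim in the Statement of the Problem, the Purpose of the Current Proposal and the hypothesis closing the Significance section all say so. The PET/CTA Study Protocol section identifies the evidence gap in the same terms: a randomised trial "to determine whether exercise or PCI provides greater improvement in myocardial perfusion has not been performed".

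Two places say something else. The rationale paragraph of the PET/CTA Study Protocol gives the objective as demonstrating that exercise training "can improve myocardial perfusion to a degree that is similar to PCI", and the same paragraph names PET myocardial perfusion reserve as the primary outcome. Key Question 2, repeated in the Statistical Analysis Plan, asks whether exercise gives secondary outcomes "in patients with CAD that are equivalent or superior to PCI".

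For Key Question 1 the Statistical Analysis Plan says "Differences within and between groups will be assessed using repeated measures ANOVA", with group and test (baseline or 1 year) as factors. Key Question 2 gets the same ANOVA. Sample Size Estimates powers the "absolute value of difference in group values for mean change divided by the standard deviation". No section gives an equivalence or non-inferiority margin, or a confidence-interval rule.

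**The concern.** A two-sided difference test can support a claim that one arm did better. When it is non-significant, it cannot support a claim that the arms did about equally well; that needs a margin fixed in advance and an interval lying inside it. With *similar* written as an objective for the primary outcome and nothing to rule out the misreading, a null result could be reported as showing that exercise matches PCI.

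A null result is not remote. The PET/CTA Study Protocol section cites a study in which "the investigators reported a 20% improvement in myocardial perfusion reserve after 14 weeks of exercise training", and a 20% gain after PCI from another study. This makes a small true difference plausible, but no more: the exercise figure comes from seven patients, and the PCI figure from one before-and-after study.

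**Working it through.** **Inputs (Sample Size Estimates).** SD 0.20 at each visit; pre-post correlation 0.65; base value 0.9; difference to detect 15%; two-sided 0.05; 80% power; 25 completers per arm; 20% dropout.

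**1. The plan's own figure.**
- SD of change = 0.20 × √(2 × (1 − 0.65)) = 0.1673 (plan: 0.167).
- Effect = 0.15 × 0.9 = 0.135. Standardised, 0.135 / 0.1673 = 0.81, as stated.
- With 25 per arm (48 df) the two-sample t-test on change has power 0.80. Enrolment is 25 / 0.80 = 31.25, so 32 per arm. The sizing reproduces.

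**2. Precision.**
- Standard error = 0.1673 × √(2/25) = 0.0473.
- 95% half-width = 2.011 × 0.0473 = 0.095. That is 0.095 / 0.9 = 10.6% of the base value, or 0.57 SD of change.

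**3. What non-significance would mean (noncentral t, 48 df).**
- True difference 0: non-significant 95% of the time.
- Exercise worse by 10 percentage points (assumed; 0.10 × 0.9 = 0.09; noncentrality 0.09 / 0.0473 = 1.90): non-significant 54% of the time.

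A non-significant result therefore does little to separate no deficit from a deficit half the size of the cited 20% PCI gain.

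**4. Smallest margin with 80% power at 25 per arm, true difference 0.**
- Non-inferiority, one-sided 0.025: 0.135 (0.81 SD of change).
- Equivalence, two one-sided 5% tests: 0.14 (0.84 SD of change).

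The planned effect is itself 0.135.

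**5. A tighter margin, for scale.** The documents give none, so I assume half the planned effect, 0.0675.
- Power at 25 per arm: 29% for non-inferiority and 0.4% for equivalence. The latter is tiny because the 90% half-width, 1.677 × 0.0473 = 0.079, already exceeds the margin.
- Completers needed for 80% power: 98 per arm (non-inferiority) or 106 per arm (equivalence). After 20% dropout, 98 / 0.80 gives 123 and 106 / 0.80 gives 133 enrolled per arm.

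**6. Baseline-adjusted analysis (ANCOVA).**
- Residual SD = 0.20 × √(1 − 0.65²) = 0.152.
- Power for 0.135 is 0.868 ignoring chance baseline imbalance and 0.861 allowing for it, against 0.80 for the change score.
- Smallest margins at 80% power, allowing for imbalance: about 0.124 and 0.129.
- Over a range of correlations, ANCOVA against change score: 0.76 against 0.65 at 0.5; 0.97 against 0.96 at 0.8.

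**Scale.** The plan gives a "standard deviation of myocardial flow reserve in similar populations of 0.20 ml/g/min both at baseline" and after treatment, yet of the outcome it says: "It is defined as the ratio of myocardial perfusion during stress to myocardial perfusion at rest". Absolute figures above inherit that unit problem. In SDs of change the comparison does not: half-width 0.57, planned effect 0.81, smallest margins 0.81 and 0.84. The same standardised margins apply to any continuous secondary outcome analysed as change with 25 per arm.

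**The case against.** The design is mostly coherent. Superiority is the stated primary aim, the two-sided test suits it, and the sizing arithmetic is right. The similarity sentence sits in a rationale for choosing PET and may be loose motivation. Key Question 2 is a disjunction, and its *superior* limb can be tested as planned. All of this stands, and it limits the point to one discordant objective on the primary outcome and one limb of a secondary question. It does not remove the point, because that sentence is worded as something to be demonstrated and *equivalent* is repeated inside the Statistical Analysis Plan.

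A reader might infer more in three places, and the documents do not support it:

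- **That the primary test is undefined, or might be the group main effect.** For the planned effect the main effect would have only about 25% power, but no section proposes to decide on it. Sample Size Estimates fixes the contrast as the difference in mean change, which in a two-arm, two-visit design is the group-by-test term.
- **That there is no comparator, so a within-arm gain would count as success.** The Principal Objective and Key Question 1 omit PCI, but the primary aim, the Purpose section and the analysis of Key Question 1 all name it. No section says a within-arm gain will be credited to exercise, although listing within-group differences beside between-group ones leaves room for it.
- **That the true difference is near zero.** The two 20% figures are too thin to establish that.

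It is also fair to say that repeated measures ANOVA is valid. Baseline adjustment is a gain in efficiency and does not solve the similarity problem.

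**Conclusion.** The concern holds in this limited form. The planned analysis can answer whether exercise and PCI differ. It cannot support the statement that the perfusion gain is similar to PCI, or the *equivalent* limb of Key Question 2. At the planned size only a margin about as large as the whole planned effect (0.135 to 0.14, or about 0.12 to 0.13 with baseline adjustment) has 80% power. If exercise achieved the anticipated 15% gain, a margin that wide would tolerate a shortfall against PCI about as large as that gain.

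These figures rest on the plan's SD, correlation and base value, a true difference of zero for the margins, and two assumptions of mine: the 10-point deficit and the half-effect margin. The conclusion in SD units does not depend on the measurement scale. The matter should be corrected, but it does not undermine the primary superiority comparison.

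**What to change.** 1. **Similarity wording.** In the PET/CTA Study Protocol, Key Questions and Statistical Analysis Plan, either delete *similar* and *equivalent*, or allow such a claim only against a justified margin fixed in advance, with a confidence-interval rule. In either case, state that a non-significant difference will not be read as similarity. The choice is the sponsor's. Deletion costs only wording, but it leaves a similarity question unanswered if that is what the sponsor wants to know. A margin narrower than about 0.12 to 0.14 would be underpowered at 25 completers per arm and would need a larger trial.
2. **Primary analysis.** In the Statistical Analysis Plan, make the primary analysis the between-arm difference in 1-year global myocardial perfusion reserve, adjusted for baseline by ANCOVA and reported with a 95% confidence interval. Treat within-arm changes as descriptive. The baseline scan is already scheduled, so no subjects, scans or tests are added.
3. **Minor clarifications.** If the repeated measures ANOVA is kept, name the group-by-test term as the primary contrast. Name PCI as comparator in the Principal Objective and Key Question 1.
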